## 1.4 Protocol Synopsis

Title	A Phase 2, Multicenter, Single-Arm Trial of CV301 in Combination with PD-1/L1 Blockade in Patients with Locally Advanced or Metastatic Urothelial Bladder Cancer
Clinical phase	Phase 2
Sponsor	Bavarian Nordic A/S 
Number of sites	Approximately 12
Vaccination dose, schedule and administration route	
Prime with MVA-BN-CV301 (nominal titer <math>1.6 \times 10^9</math> Inf.U) given subcutaneously (SC) on Day 1 and Day 22. One dose = four 0.5 mL injections. One injection = nominal titer <math>4 \times 10^8</math> Inf.U in 0.5 mL.
 
Boost with FPV-CV301 (nominal titer of <math>1 \times 10^9</math> Inf.U in 0.5 mL, given SC every 21 days for 4 doses (on days 43, 64, 85, and 106), followed by boosts every 6 weeks until 6 months on trial (i.e., days 148 and 190), then every 12 weeks until completion of 2 years. One dose = one 0.5 mL injection.
 
Atezolizumab fixed dose of 1200 mg intravenous on Day 1 of each 21-day cycle. No dose reduction permitted.

Trial duration	Approximately 104 weeks before starting the long term follow up.
Trial Population	
Patients with Locally Advanced or Metastatic Urothelial Cancer (UC) including bladder, ureter, renal pelvis and urethra.
 
Cohort 1: Ineligible for cisplatin-containing chemotherapy (first-line treatment)
 
Cohort 2: Previously treated with standard first-line cisplatin-based chemotherapy, PD-1/L1 Naïve (second-line treatment)

Number of Subjects:	Approximately up to 68
Primary objectives	Objective Response Rate (ORR; Complete Response [CR] + Partial Response [PR] Rate) as per Response Evaluation Criteria in Solid Tumors version 1.1 (RECIST 1.1)

Secondary objectives	Progression-Free Survival (PFS)  Overall Survival (OS)  Duration of Response  Safety of the treatment combination of CV301 with atezolizumab

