Exploratory objectives	Analysis of biopsy tissue for differences between pre- and post-treatment samples correlation to patient survival e.g.: 

• T cell receptor (TCR) clonality

• Tumor-Infiltrating-Lymphocytes (TILs)

• Protein expression for e.g. Programmed Death Ligand 1 (PD-L1) and other biomarkers

• Gene expression profiling for molecular subtyping

 Analysis of tumor DNA for Tumor mutational burden; DNA damage response gene mutations, MSI status, MMR deficiency status  Analysis of peripheral blood mononuclear cells (PBMCs) / serum for differences between pre- and post-treatment samples correlation to patient survival e.g.: 

• Antigen-specific immune responses to carcinoembryonic antigen (CEA) and mucin-1 (MUC-1) as well as to other tumor-associated antigens (TAAs) to assess antigen cascade

• Immunophenotyping of immune cell subsets by flow cytometry

• Soluble biomarkers (e.g. cytokines and classical tumor markers)

• TCR clonality

• PD-1/L1 staining

Primary endpoint	Proportion of subjects with a confirmed OR (CR+PR) as per investigator assessment according to RECIST 1.1.

---

Secondary endpoints	
Safety of the combined treatment as measured by:
 

• Adverse Events (incidence, severity, and seriousness of treatment emergent adverse events [TEAEs])

• Laboratory Measures (summaries and shifts from baseline)

• Vital Signs (summaries)

 
OS defined as the time from start of treatment to the time of death from any cause.
 
Duration of response defined as the time from the initial occurrence of documented complete response (CR) or partial response (PR) (whichever occurred first) until documented disease progression or death due to any cause on trial, whichever occurred first.
 
PFS defined as the time from start of treatment to the first event of death or progressive disease (PD) per RECIST 1.1.
 
Percentage of participants with OS and PFS at 6 (PFS only), 9 (PFS only), 12, 18 and 24 months.
 
Immune-related Response Criteria assessment of response rate per iRECIST, delayed responses (pseudo-progressions), duration of response and PFS.

Trial design	Phase 2, Multicenter, Single-Arm, 2 Cohorts, Two-stage

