- Subjects who are discontinued from treatment in the absence of disease progression (e.g., subjects removed for unacceptable toxicity or subject/investigator discretion) should undergo repeat imaging and tumor response assessments until disease progression is documented. Radiological assessment should be continually performed as per schedule. It is recommended that subsequent therapy not be instituted until disease progression is documented.

If the subject is unwilling or unable to come to the clinic for a final EOT assessment, all efforts by the investigator and/or site staff to contact the subject need to be fully documented in the Investigator Site File and the End of Treatment eCRF page, as instructed. Subjects that are withdrawn from treatment will enter the LTFU period.

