#### **4.2.5.2 Discontinuation from Long Term Follow-up**

All subjects will be followed until death, via telephone contacts at 3 month intervals, to evaluate OS unless the trial is suspended or discontinued. The length of the LTFU is planned to be 2 years, unless all subjects achieve their OS endpoint prior to the end of the 2-year period. If a subject chooses to withdraw from trial survival follow-up, this request must be documented in the source documentation and signed by the investigator. If the subject withdraws from participation in long term telephone follow-up, the trial staff may use a public information source (such as county records) to obtain information about survival status only.

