### **4.3 Trial Duration**

- Screening – approximately 4 weeks

- Treatment Phase – approximately 100 weeks
- Long Term Follow-up – Until all subjects achieve the OS endpoint, or a maximum time of up to 2 years

The total duration of the trial for each subject is up to 4 years.

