### **9.7.2.2 Overall Survival**

OS is defined as the time interval from first treatment to death of any cause. Subjects who are alive will be censored at the last known date subject is alive. The 12-month OS rate and the product-limit estimate of median survival, as well as their 90% confidence intervals will be summarized. A Kaplan-Meier curve will summarize OS graphically. The 18-month and 24-month survival rates will also be provided along with their 90% CIs.

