## **9.12 Timing of Analyses**

The first post-treatment objective radiographic response assessment by the investigator will occur approximately 10 weeks after first treatment, with the second occurring 12 weeks later at the Week 22 visit. For subjects who have completed multiple scans, the best objective response will be used.

If at least 4 objective responses in Cohort 1 (or 3 objective responses in Cohort 2) are observed in the FAS prior to the end of Stage 1, enrollment of Stage 2 subjects will continue regardless of the full enrollment of the EE Set. If the results of Stage 1 are unclear based on full enrollment of Stage 1 in the FAS, enrollment will continue until the full Stage 1 sample size is reached for the EE Set. If success is not possible in Stage 1, even with continuing enrollment until the full EE set was reached and all additional subjects were responders, the cohort will be discontinued without meeting full enrollment of the EE Set. In addition, the timing of the initiation of Stage 2 in a cohort need not depend on the completion of Stage 1 in the opposite cohort.

The end of Stage 2 analyses will again be based on best objective response outcomes. If the required number of responses are observed for a positive outcome in Stage 2 for the FAS, enrollment will be stopped and the trial will be declared a success. If it is unclear if the study is successful based on the FAS subjects, additional subjects will be enrolled until the full sample size for Stage 2 is reached in the EE Set. Because objective radiographic response rates may increase with further follow up, the data may be analyzed with updates if subsequent follow up demonstrates additional objective responses.

Final analyses will occur when all subjects have either completed the 2-year treatment period, or have progressed.

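### The final analyses are timed by treatment completion or progression, and no OS data cutoff is stated, so the 24-month OS estimate can be made before some living subjects have been followed for 24 months

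*Protocol*

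**What the plan says.** Protocol 9.12 gives one rule for the end of the trial: "Final analyses will occur when all subjects have either completed the 2-year treatment period, or have progressed". The same section allows later data updates, but they are optional and concern additional objective responses.

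OS is a secondary endpoint. The Protocol synopsis (1.4) lists "Percentage of participants with OS and PFS at 6 (PFS only), 9 (PFS only), 12, 18 and 24 months", and Protocol 9.7.2.2 adds: "The 18-month and 24-month survival rates will also be provided along with their 90% CIs". On censoring it says: "Subjects who are alive will be censored at the last known date subject is alive". SAP 4.4.5.2.2 repeats the milestones and the Kaplan-Meier analysis. It states no data cutoff.

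Survival follow-up goes well beyond treatment. Protocol 4.2.5.1 says: "Subjects that are withdrawn from treatment will enter the LTFU period". Protocol 4.2.5.2 says: "The length of the LTFU is planned to be 2 years", with telephone contacts every 3 months. The SAP's definition of the long-term follow-up period is similar and ties no analysis to it.

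Treatment length is described in three ways: "Treatment Phase – approximately 100 weeks" (Protocol 4.3), "Approximately 104 weeks before starting the long term follow up" (synopsis) and a 2-year period (Protocol 9.12). The visit schedule ends at Week 100, Day 694.

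**The concern.** The rule suits ORR, PFS and duration of response, which are settled by progression or by the end of treatment. It does not suit a 24-month survival rate, for two reasons.

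- A last-enrolled subject who completes treatment at Day 694 has not yet reached 24 months.
- A late enrollee who progresses at an early scan satisfies the rule immediately. That subject may be alive and moving into survival follow-up, but no longer holds the analysis back. OS is then censored wherever the last contact happened to fall.

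The cohorts have at most 33 and 35 subjects and are analysed separately, so a few censored survivors matter to the number at risk at month 24. The survival contacts that would supply the missing follow-up are already planned, but no specified OS analysis uses them. Leaving the OS cutoff open in an open-label trial also means that its date could be chosen after data have been seen.

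Separately, a subject who dies, withdraws or is lost without progression meets neither limb of the rule as written.

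**Working it through.** **1. The plan's own timeline.** Screening 4 weeks + treatment 100 weeks + follow-up 104 weeks = 208 weeks = 3.99 years. This agrees with the 4-year maximum per subject in Protocol 4.3. Week 100 is Day 99 × 7 + 1 = 694, as scheduled.

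**2. Gap to month 24.** 694 / 30.4375 = 22.8 months. 24 months is 730.5 days, so the gap is 730.5 − 694 = 36.5 days, or 1.2 months. Over the SAP's Day 680 to 708 window it is 50.5 to 22.5 days. If treatment lasts a full 24 months, this gap disappears.

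**3. If the last enrollee stays on treatment to Day 694.** Only subjects entered in the last 1.2 months of accrual fall short. With uniform accrual of 68 subjects over A months, that is 68 × 1.2 / A: about 14, 7, 4.5 or 3 subjects for A = 6, 12, 18 or 24. Many of these may already have died.

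**4. Allowing for early progression.** Inputs:

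- From the documents: N = 68 or 27 (SAP 4.1), and 12-month PFS of 16.8% (Protocol 2.1, second-line pembrolizumab).
- Assumed: uniform accrual over A months, exponential post-progression survival with median 7 months, 20% of PFS events being deaths, and a long-term progression-free fraction π of 0 or 10%.

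For subject i with entry time e and progression time P, and treatment length L:

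- progression hazard = −ln[(0.168 − π)/(1 − π)] / 12, which is 0.149 per month for π = 0 and 0.215 for π = 10%;
- analysis time T = the maximum over subjects of e + min(P, L), with L = 22.8 or 24 months;
- available follow-up f = T − e;
- subjects that count: f < 24 and still alive at f.

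Mean results for N = 68 (20,000 replicates; ranges run over A = 12, 18, 24):

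| L (months) | π | f < 24 months | Alive and censored before 24 | At risk at 24, against full follow-up |
|---|---|---|---|---|
| 22.8 | 0 | 27–38% | 5.0–6.2 | 7.7–9.0 against 12.4 |
| 22.8 | 10% | 18–23% | 3.3–3.9 | 11.5–12.3 against 15.0 |
| 24 | 0 | 24–31% | 4.1–4.6 | 9.0–9.7 against 12.4 |
| 24 | 10% | 12% | 1.4–1.6 | 13.8–13.9 against 15.0 |

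The third column overstates the problem, because it includes subjects who have already died and so contribute fully to OS. The fourth column is the relevant one. Of those censored survivors, at most about 1.6 would die by month 24.

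**5. Both cohorts stopped at Stage 1 (N = 27, accrual 8 to 12 months, L = 22.8).** With π = 0, 59–67% have f < 24. Across π = 0 and 10%, the expected number at risk at month 24 falls from about 5–6 to about 2–4.

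**6. Sensitivity.** With 12-month PFS of 25%, 12% long-term progression-free and median post-progression survival of 10 months, the number alive and censored before 24 months is 4.0–5.3 of 68 for L = 22.8 and 2.1–2.2 for L = 24 (accrual 12 to 24 months). With 6-month accrual and L = 22.8 it reaches 7.7.

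**7. Later deaths.** Across scenarios with accrual of 6 to 24 months, on average 2 to 7 of 53–65 deaths at N = 68 fall after the analysis but within long-term follow-up.

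**The case against.** **Effect on the estimate.** OS is secondary and descriptive, with no hypothesis test. Kaplan-Meier handles administrative censoring, so provided entry date is unrelated to prognosis there is no bias. This stands, and it limits the severity.

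**Size.** A reader might infer that many subjects cannot reach the milestone. The documents do not support that: they give no accrual period, and most subjects with short available follow-up will have died. A pause between stages would give early enrollees more follow-up, and a full 24-month treatment period shrinks the effect. The 16.8% figure is second-line, whereas the first-line reference trial for Cohort 1 had 12-month survival of 75% (Protocol 2.1). The Stage 1-only scenario matters least, because 24-month OS in two cohorts stopped for futility has little decision value.

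**Unused deaths.** A reader might infer that deaths in follow-up will go unanalysed. The text does not go that far. No later OS analysis is specified, but none is excluded, and SAP 4.4.5.2.2 expects loss-to-follow-up and withdrawal status to be revised over time.

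**Tail of the curve.** It is tempting to cite Protocol 2.8.2 on separating Kaplan-Meier tails as a reason why late OS is critical here. That sentence concerns PFS and a comparison between arms. The same section calls the benefit pattern of the combination uncertain.

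**A condition that can never be met.** Read literally, one death without progression would block the analysis for ever. The intent is clear enough: Protocol 9.7.2.1 counts death as a PFS event, Protocol 4.2.5.1 continues imaging after early discontinuation, and SAP 2.6.4.1 allows for early discontinuation at the interim. This is a wording gap.

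What remains is that neither document gives an OS cutoff, and the one stated rule can fall before month 24 for living subjects.

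**Conclusion.** The point holds as a low-severity gap that is cheap to close. The final-analysis rule is not linked to survival follow-up, and it can leave about 3 to 6 of 68 subjects alive and censored before month 24 (about 1.5 to 5 if treatment lasts a full 24 months). The expected number at risk at month 24 then falls from about 12–15 to about 8–12 of 68, across both cohorts together, if treatment ends at Day 694. These figures rest on assumed accrual, post-progression survival and progression-free fraction; only the 16.8% PFS rate and the sample sizes come from the documents. The consequence is a less precise 24-month OS estimate. The ORR test and the stage decisions are unaffected.

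**What to change.** 1. Keep the current rule in Protocol 9.12 for ORR, PFS and duration of response, reworded so that death, withdrawal and loss to follow-up also satisfy it.
2. Add to Protocol 9.12 and the SAP: *The OS milestones and median OS are reported from a data cut taken when every subject has died, withdrawn, been lost to follow-up, or been followed for at least 24 months from first dose.*
3. Add an OS update at the end of long-term follow-up. The cut in item 2 alone would still leave out deaths after it.
4. Reconcile the 100-week, 104-week and 2-year statements of treatment length, since the timing of the rule depends on them.

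The second item removes administrative censoring before month 24. If the last-enrolled subject completes treatment, that cut comes 36.5 days after the Day 694 visit; the delay is longer if late enrollees progress early. The cost is a few sentences in two documents, one later OS table with its update, and a later final OS report. The survival contacts are already planned.

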## **9.13 Changes in Statistical Methods**

All changes in statistical methods from that described in the Statistical Analysis Plan will be documented in the Clinical Study Report.

# **10 Ethical Aspects**

## **10.1 Ethical and Legal Regulations**

This trial will be conducted in a manner consistent with the principles that have their origin in the Declaration of Helsinki and in accordance with FDA regulations (21 CFR § 11, 50, 54, 56, and 312), with the ICH GCP guidelines (ICH E6), as well as with any and all applicable federal, state and/or local laws and regulations.

## 10.2 Approved by IRB

Before enrollment of subjects into the clinical trial, as required by federal regulations (21 CFR § 56), ICH GCP and local regulations, the current protocol and ICF will be reviewed and approved by an appropriate IRB. A letter documenting the IRB or IEC approval must be received by the sponsor before the initiation of the trial at a clinical site. Amendments to the protocol will be subject to the same requirements as the original protocol.

The Investigator will submit a progress report at least once yearly to the IRB. However, the frequency of these reports will depend on IRB requirements. As soon as possible after completion or termination of the trial, the Investigator will submit a final report to the IRB per the IRB requirements, and in compliance with FDA regulations and ICH GCPs.

The Investigator, the sponsor, or designee shall promptly notify the IRB or IEC of any SAEs, or any other information that may affect the safe use of the trial drug during the course of the trial, per the IRB local requirements, and in compliance with FDA regulations and ICH GCPs.

Copies of all correspondence between the investigator and the IRB must be forwarded immediately to the Sponsor or designee. In case of withdrawal of IRB approval of the trial, the Sponsor or designee has to be contacted immediately by facsimile, e-mail or telephone.

## 10.3 Confidentiality and Data Protection

Information on maintaining subject confidentiality in accordance with individual local and national subject privacy regulations must be provided to each subject as part of the informed consent process either as part of the ICF or as a separate signed document (for example, in the US, a site-specific Health Insurance Portability and Accountability Act [HIPAA] consent may be used).

The Investigator or designee must explain to each subject that for the evaluation of trial results, the subject's protected health information (PHI) obtained during the trial may be shared with BN and its designees, regulatory agencies, and IRBs. As the trial Sponsor, BN will not use the subject's PHI or disclose it to a third party without applicable subject authorization. It is the Investigator's or designee's responsibility to obtain written permission to use PHI from each subject. If a subject withdraws permission to use PHI, it is the Investigator's responsibility to obtain the withdrawal request in writing from the subject and to ensure that no further data will be collected from the subject. Any data collected on the subject before withdrawal will be used in the analysis of trial results.

During the review of source documents by the monitors or auditors, the confidentiality of the subject will be respected with strict adherence to professional standards and regulations.

## 11 Informed Consent

The investigator is responsible for ensuring that the subject understands the potential risks and benefits of participating in the trial, including answering any questions the subject may have throughout the trial and sharing in a timely manner any new information that may be relevant to the subject's willingness to continue his or her participation in the trial.

No subject can participate in the trial without first having given informed consent in writing. The investigator or his delegate will inform the subject clearly and completely, verbally and in writing, about the purpose, procedures and the potential benefits and risks of participation in the trial prior to the initiation of any trial specific procedure. The subject will also be informed of the potential future use of biological samples collected during the trial.

The ICF will be used to explain to the subject in simple terms the potential risks and benefits of trial participation and to document that the subject is satisfied with his or her understanding of the risks and benefits of participating in the trial.

The investigator is responsible for ensuring that informed consent to participate in the trial is given by each subject (or their legal representative). This includes obtaining the appropriate signatures and dates on the ICF prior to the performance of any protocol procedures and prior to the administration of trial drug.

One signed copy of the ICF (including HIPAA) must be given to each subject and one signed copy must remain in the Investigator Site File and be available for verification by the monitor, Sponsor/CRO auditor or competent regulatory authorities at any time.

Subjects must be informed unequivocally that they may refuse participation in the trial and that they may withdraw from the trial at any time and for whatever reason and that withdrawal of consent will not affect their subsequent medical treatment or relationship with the treating physician.

Subjects also consent to authorize the monitor, quality assurance personnel and regulatory authorities to inspect source documents for data verification and quality assurance purposes. Such verifications will always be conducted at the clinical trial site and under the ethical supervision of the investigator. To the degree possible, confidentiality of the subject's PHI will be maintained.

The Informed Consent will be prepared in accordance with ICH GCP guidelines and must be approved by the appropriate IRB.

## **12 eCRF and Retention of Records**

### **12.1 eCRF**

eCRFs will be used to collect the clinical trial data and must be completed for each screened subject. All data must be accurately recorded such that the information matches the data contained in subject's medical records (e.g., physicians' notes, nurses' notes, clinic charts, and other trial-specific source documents). Authorized trial site personnel (i.e., listed on the Delegation of Authority form) will complete training based on the electronic data capture (EDC) system for the trial, as well as complete the trial-specific eCRFs according to the eCRF Completion Guidelines (provided as a separate document). The Investigator will ensure that the eCRFs are accurate and completed within 5 days of each subject's visit. At all times, the Investigator has final responsibility for the accuracy and authenticity of all clinical data.

The eCRFs exist within an EDC system with controlled access managed by BN or its authorized representative for this trial. Trial staff will be appropriately trained in the use of trial-specific eCRFs and application of electronic signatures before the start of the trial, and before being given access to the EDC system. Original data and any changes of data will be recorded using the EDC system, with all changes tracked by the system and recorded in an electronic audit trail per CRF. Note, only changes entered into the eCRF fields, themselves, can be used for reporting of trial results. Information entered into the change logs (for example, query responses) will be for documenting reasons for changes only.

The Investigator attests that the information contained in the eCRFs is true by providing electronic signature within the EDC system. After database lock, the Investigator will receive a copy of the subject data (e.g., paper, CD-ROM or other appropriate media) for archiving at the clinical trial site.

